3.1 Overview of Proposed Research Design

This investigation employs a randomized controlled trial (RCT) study design. Participants will be randomized into either precision pharmacotherapy, where they will receive a personally-tailored recommendation for a TUD medication based on their NMR plus standard care, or to standard care only. Standard care will adhere to the Ask-Advise-Connect model where participants are asked about tobacco use, advised to quit smoking, offered a choice of FDA-approved TUD medication and offered a referral to the Delaware Quitline for access to counseling services and medications.

Upon enrollment into the study, the research assistant will verify demographic data, administer a baseline survey, and coordinate testing for the NMR at their in-person intake visit. Patients will be randomized to the precision or standard care arms in a 1:1 ratio. Following receipt of the NMR test results and randomization, the research assistant will follow-up with a pre-quit telephonic visit to review procedures with participants. For standard care, the research assistant will provide information on FDA-approved TUD medications and offer to coordinate the process of starting on a medication of the participants' choice (i.e., nicotine patch or varenicline), which participants can decline. Participants randomized to precision pharmacotherapy will be provided with their NMR result, information on how NMR impacts TUD treatment, and a personalized recommendation for medication based on their NMR result (i.e., varenicline for faster metabolizers, nicotine patch for slower metabolizers). Similar to standard care procedures, participants will be offered either the nicotine patch or varenicline and will not be required to choose the medication based on their personalized recommendation, or any medication. For participants in both conditions who opt for medication, per participant preference, medications can be prescribed by the study physician ([name]) or the patient can be referred to the Delaware Quitline for no-cost medications, a free service available to all Delaware residents. A 1-week follow-up telephonic visit will be conducted to collect data related to medication use, quit date or smoking rate, and side-effects. Finally, a 1-month follow-up in-person visit will be arranged to complete a follow-up survey and to assess smoking status.

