Document: Statistical Analysis Plan

Document Date: March 5, 2020

Official Study Title: A Pilot Pragmatic RCT of a Hospital-based Precision Pharmacotherapy Smoking Cessation Program

NCT#: NCT04897607

Statistical Analysis Plan

Specific Aim 1: *The proposed trial will be acceptable to underserved smokers as measured by the proportions and demographic characteristics of patients who enroll (H1.1), accept pharmacotherapy (H1.2), and complete follow-up (H1.3).*

Descriptive statistics and 95% confidence intervals will be used to summarize the feasibility metrics, namely the numbers and proportions of patients who: 1) were approached, 2) deemed eligible, 3) enrolled, 4) accepted pharmacotherapy, and 5) completed follow-up. To gain a sense of whether study participants may be considered representative of the larger population of ChristianaCare smokers as measured by race and area-level measures of SES, chi-square tests and Wilcoxon rank tests will be conducted. Race is routinely collected for all admitted patients and will permit a comparison between trial participants and the larger population of ChristianaCare smokers. However, no individual-level measures of SES are routinely collected for admitted patients and therefore will not allow for a comparison between trial participants and the larger population. Therefore, census tract measures of poverty (e.g. employment status, income, and education) based on participant residence will be used as a proxy for individual-level SES. The residential addresses for the larger population of ChristianaCare smokers has been previously geocoded and linked to census tract poverty measures,⁴⁸ which will be used to compare the proportions of participants in this trial who reside in each census tract strata.

Specific Aim 2: *Patients assigned to precision care will more readily accept pharmacotherapy (H2.1), achieve greater treatment matching (H2.2), and demonstrate improved abstinence rates (H2.3).*

Three sets of logistic regression models will be used to compare precision pharmacotherapy vs. standard care for each of the binary effectiveness outcome measures: acceptance of pharmacotherapy, treatment matching, and abstinence. Models will adjust for demographics and other covariates, including age, race/ethnicity, nicotine dependence, and indicators of SES (employment status, income, and education).

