Exploratory Aim: *Precision pharmacotherapy will improve patient outcome expectancies related to medication effectiveness and safety/side effects, which will be associated with greater use of pharmacotherapy (H3.1) and abstinence (H3.2). Higher rates of treatment matching in precision care will mitigate the reductions in abstinence rates for low-SES/racial minority smokers compared to standard care (H3.3).*

Mediation analyses. Two sets of logistic regression models will be used to evaluate whether patient outcome expectancies mediate the relationship between treatment assignment (precision vs. standard) and the outcome measures use of pharmacotherapy and abstinence. In the first step for each model, treatment condition will be used to predict the outcome measures, adjusting for the same covariates used above. In the second step, patient outcome expectancies will be used to predict the outcome measures, again adjusting for covariates. If both treatment condition and treatment expectancies are significantly associated with outcome measures, a third step will include both predictors to formally test for partial or complete mediation by assessing whether the inclusion of patient outcome expectancies reduces or eliminates the effect for treatment assignment.

Moderation analyses. A series of logistic regression models will be used to evaluate whether greater treatment matching mitigates (i.e., moderates) the lower rates of abstinence typically seen among low-SES/racial minority patients in usual care. The model will include the predictors of treatment matching (dummy coded as yes/no based on whether the participant used the medication matched to their nicotine metabolism rate: NRT for slower metabolizers, varenicline for faster metabolizers), measures of SES (e.g., years of education), and the product of these predictors. If the product, or interaction term, significantly predicts abstinence, that would provide evidence that treatment matching has differential impacts based on the SES of the participant. Post hoc analyses will be employed to describe the nature of the interaction. A

similar, albeit multilevel approach will be used to test for interaction between area-level variables (e.g., census tract poverty levels, tobacco outlet density) and treatment matching.

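### The exploratory moderation model enters treatment matching without drug or metabolizer main effects, so its matching-by-SES product can be non-zero, in either direction, with no matching effect

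*SAP*

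**What the plan says.** The SAP's Exploratory Aim, under Moderation analyses, plans logistic models for abstinence. It says "The model will include the predictors of treatment matching (dummy coded as yes/no", where yes means that the participant used the drug paired with their metabolizer group: "NRT for slower metabolizers, varenicline for faster metabolizers". The precision arm's recommendation in Protocol section 3.1 follows the same rule ("varenicline for faster metabolizers, nicotine patch for slower metabolizers"). The remaining terms are "measures of SES (e.g., years of education), and the product of these predictors". If the product is significant, the SAP concludes "that would provide evidence that treatment matching has differential impacts based on the SES of the participant". A multilevel version is planned for area-level variables such as tract poverty.

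No term is listed for drug used, metabolizer group or arm. The mediation paragraph just above says "adjusting for the same covariates used above"; the moderation paragraph does not repeat this. Carrying the Aim 2 covariates over would not fill the gap, because that list, "including age, race/ethnicity, nicotine dependence, and indicators of SES (employment status, income, and education", has no drug or metabolizer term. Under Protocol section 3.3, participants in both arms choose either drug or decline medication.

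**The concern.** Matching is built from two variables, drug and metabolizer group, and is their interaction collapsed to one indicator. If it is entered without its components, its coefficient also absorbs whatever drug or metabolizer group does by itself. When most users are faster metabolizers, matched users are mostly on varenicline and unmatched users mostly on patch, so an overall difference between the drugs appears as a matching effect. On the literal wording, people who take no drug are coded as unmatched, so any drug versus none is mixed in as well.

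If the amount absorbed differs between SES levels, the difference goes into the product. The SAP attaches its only interpretation rule to that product, so an SES difference in metabolizer mix, uptake or drug effect could be reported as matching working differently by SES.

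**Working it through.** **Inputs.** From the documents: about 100 participants (Protocol 2.0), free choice of drug or none (Protocol 3.3) and the model terms (SAP). The SAP gives no design figure for this model, so there is none to reproduce. The only quit rate in the documents is a cited review's, rarely above 25% (Protocol background). The share of faster metabolizers, abstinence by drug, uptake and drug choice are all assumptions. SES is taken as binary for simplicity.

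**1. What the coefficient should be.** Give each drug and each metabolizer group its own main effect on the log-odds scale, and let d be the matching coefficient. The effect of being a faster metabolizer is then m + d on varenicline and m − d on patch. The drug-by-metabolizer interaction among users is (m + d) − (m − d) = 2d, so d measures matching only when the main effects are in the model.

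**2. Planned model, no matching effect, users only, drug chosen evenly.** Let f be the share of faster metabolizers. Varenicline makes up f of the matched and 1 − f of the unmatched. With abstinence of 35% on varenicline and 20% on patch, whatever the metabolizer group:
- matched: 0.20 + 0.15f; unmatched: 0.20 + 0.15(1 − f)
- high SES, f = 0.70: 0.305 and 0.245; OR = (0.305/0.695)/(0.245/0.755) = 1.35
- low SES, f = 0.45: 0.2675 and 0.2825; OR = (0.2675/0.7325)/(0.2825/0.7175) = 0.93
- ratio of ORs, high over low = 1.352/0.9275 = 1.46; with the mix swapped, 1/1.46 = 0.69

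**3. Other assumptions, still with no matching effect.**

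| Abstinence | What differs by SES | OR low | OR high | Ratio |
|---|---|---|---|---|
| varenicline 25%, patch 15% | f 0.40 low, 0.70 high | 0.88 | 1.28 | 1.46 |
| same | f 0.30 low, 0.75 high | 0.78 | 1.37 | 1.76 |
| same, no drug 10%, non-users coded unmatched, f 0.60 | uptake 40% low, 80% high | 1.90 | 1.40 | 0.73 |
| patch 15%, f 0.70 | varenicline 15% low, 30% high | 1.00 | 1.41 | 1.41 |
| as row 3, uptake 60% | nothing | 1.65 | 1.65 | 1.00 |

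A metabolizer main effect can leak too. If faster metabolizers quit at 12% and slower at 22% whatever the drug, with half of users faster, the matching OR is 1.33 when 30% of users choose varenicline and 0.75 when 70% do. If choice differed in that way between SES levels, the false ratio would be 0.75/1.33 = 0.57 or its inverse.

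**4. Adding terms (large-sample fits).** With drug main effects, the product OR returns to 1.00 in every scenario with a common drug effect. A metabolizer term alone does not achieve this: in the first row the ratio stays at 1.46. When the drug effect varies by SES (fourth row), main effects leave 1.42. It is 1.00 only once drug-by-SES and metabolizer-by-SES terms are also in the model.

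**5. At the planned size.** In 1,200 simulated trials of the first row's setting with 100 participants, the planned product was significant at 0.05 in 4.2%. With 1,000 participants it was significant in 20%, falling to 4.8% after adding drug and metabolizer terms. In 2,000 Firth-fitted trials (100 enrolled, 80% users, the rates in step 2), the mean product was −0.36 (SD 1.04) as planned and 0.02 (SD 1.12) with the main effects. The root mean squared errors are √(1.04² + 0.36²) = 1.10 and √(1.12² + 0.02²) = 1.12. Two further settings gave 1.16 versus 1.15 (users only) and 0.99 versus 1.00 (non-users included).

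**The case against.** The strongest reply is that this is an exploratory analysis in a pilot of about 100 people, that nothing in the documents says metabolizer mix differs by SES, and that the correction does not improve accuracy at this size. All of that stands, and it limits the severity. It does not rescue the interpretation rule, because the bias does not shrink with sample size and no other text supplies the missing terms.

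A reader might infer four stronger things that the documents do not support:
- *The model will manufacture support for H3.3.* H3.3 says "Higher rates of treatment matching in precision care will mitigate the reductions in abstinence rates" for low-SES and minority smokers. In the step 2 example the false OR is 1.35 in high SES and 0.93 in low SES, which counts against H3.3. The opposite mix would favour it. The documents do not indicate either.
- *The false-positive rate is inflated.* At about 100 participants it is not: 4.2% in the simulated case.
- *Omitting arm distorts the product.* If only arm affects abstinence (15% versus 25%, with 50% versus 80% matched), the matching OR is 1.23 without an arm term and 1.00 with it. That is the main effect, which the SAP does not interpret. No such bias was shown for the product.
- *Main effects alone are a cure.* They are not when the drug effect itself varies by SES (1.41 before, 1.42 after).

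**Conclusion.** The point holds as a minor one, for the exploratory aim only. The product is the sole interpreted term, and it can be non-zero in either direction without any matching effect. Under the assumed rates and mixes the false ratio of odds ratios runs from 0.57 to 1.76, with 1.46 in the worked example. It is 1.00 when metabolizer mix, uptake, drug choice and abstinence by drug are the same at each SES level. The sizes rest entirely on assumptions, since the documents give none of these quantities. What follows from the SAP text alone is that a significant product does not by itself show what the SAP says it would show. In a trial of this size the consequence is a biased estimate that may be misread and carried into later work.

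**What to change.** In the SAP's moderation paragraph, for both the individual-level and the area-level models:
- Add main effects for drug used (varenicline, patch, none) and metabolizer group, so that matching is estimated as their interaction. The level for no drug also settles how non-users enter the model.
- Add drug-by-SES and metabolizer-by-SES terms, in the main fit or as a stated sensitivity analysis.
- Use a Firth-penalised fit, because quitters will be few.
- State that a significant product from the model without these terms will not be read as evidence that matching works differently by SES.
- An arm term is optional.

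**Cost.** SAP wording only: drug used and metabolizer group are already needed to code matching. The main effects add three coefficients (two for drug, one for metabolizer group), giving six slopes instead of three. With one SES measure, the SES interactions add three more, giving nine. At 25% abstinence, 100 participants yield about 25 quitters, or roughly four per slope (25/6) and fewer than three (25/9). The main effects raise the SD of the product slightly (1.04 to 1.12) and leave its root mean squared error about unchanged. With non-users included, the SES interactions raise that error from about 1.00 to 1.15, which is a reason to consider keeping them as a sensitivity analysis.

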3.3 Study Procedures & Data Collection

The following study procedures will be implemented. A description of the measures used to collect data during these procedures is provided below.

- **Intake Session (completed during clinic visit)**
 - Participants will complete a self-report survey of demographics, smoking history, and beliefs about the use of smoking cessation aids.
 - **[Women only]** A pregnancy screen will be administered for women capable of becoming pregnant (55 and under). NOTE: For safety reasons, pregnant women will not be eligible to participate in the research study.
 - The research assistant will complete the blood draw to be used for a nicotine metabolite ratio (NMR) test and arrange for the sample to be transported to the laboratory for processing.
- **Randomization:** Following completion of the 'intake session' and receipt of NMR testing results, participants will be randomized in a 1:1 ratio to either of the following conditions:
 - **Treatment Plan Option 1 (Standard Care):** Standard smoking cessation counseling will be offered + participant choice of nicotine patches or varenicline. Participants are also free to decline either medication.
 - **Treatment Plan Option 2 (Precision Pharmacotherapy):** Standard smoking cessation counseling will be offered + a recommendation to take either the nicotine patch or varenicline based on the results of the NMR test. Regardless of the recommendation, it would still remain the participant's choice to be prescribed either nicotine patches or varenicline. Participants are also free to decline either medication.
- **Pre-Quit Telephonic Visit:** This visit will take place after the NMR results have been received and randomization is complete, approximately 7-14 days following the intake session (depending on lab processing time).

- Participants will be informed of their treatment condition, including the recommended medication if assigned to 'treatment plan option 2' (i.e., the precision pharmacotherapy arm).
- Participants will be offered their choice of either the nicotine patch or varenicline. Participants will be reminded that taking medication is not a condition of participation in the study. In addition, participants assigned to 'treatment plan option 2' (i.e., the precision pharmacotherapy arm) will not be required to accept only the medication recommended to them based on the results of NMR testing.

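### The exploratory moderation model groups non-users of medication with users of the other drug, so its product term is not evidence about matching as such; and H3.3 has no planned arm-by-SES or arm-by-race estimate

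*SAP*

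**What the plan says.** The SAP's Exploratory Aim states H3.3 as "Higher rates of treatment matching in precision care will mitigate the reductions in abstinence rates for low-SES/racial minority smokers compared to standard care". The paragraph on moderation analyses then describes a logistic model for abstinence with three kinds of predictor: treatment matching, measures of SES (years of education is the example, so SES may be continuous), and their product. Matching is "dummy coded as yes/no based on whether the participant used the medication matched to their nicotine metabolism rate". The stated inference is "If the product, or interaction term, significantly predicts abstinence, that would provide evidence that treatment matching has differential impacts" according to the participant's SES. A multilevel version crosses area-level variables with matching.

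Protocol section 3.1 says that participants given a recommendation "will not be required to choose the medication based on their personalized recommendation, or any medication". Section 3.3 says, for each arm, "Participants are also free to decline either medication", and section 3.2 makes clear that accepting medication is not required for taking part. Non-users therefore stay in the analysis set.

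Under Specific Aim 2 the SAP lists the "binary effectiveness outcome measures: acceptance of pharmacotherapy, treatment matching, and abstinence". Each is compared between arms, with race/ethnicity and SES as adjustment covariates only.

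**The concern.** There are two separate gaps between what is modelled and what is to be concluded.

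- **Coding.** Using a drug and using the matched drug are different things, and Aim 2 treats them as different outcomes. The moderation model has one indicator for both. Its no group mixes mismatched users with non-users, in a proportion that can differ by SES. A contrast between the matched group and that mixture can depart from 1, and can depart by different amounts in low and high SES, when being matched does nothing. The plan would read this as a differential impact of matching.
- **Contrast.** H3.3 compares precision care with standard care in low-SES and racial minority smokers. Every listed interaction is with matching, which arises after randomisation, is chosen by the participant, and occurs in both arms. No model has an arm-by-SES or arm-by-race term, and race is not among the moderation predictors listed.

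At stake is how an exploratory estimate is interpreted, and whether H3.3 gets any randomised estimate at all.

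**Working it through.** The SAP gives no rates, power or significance level for this analysis, so there is no figure to reproduce. From the documents come the coding, the right to decline, the model terms and the sample of about 100 (protocol section 2.0). All rates below are assumptions.

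**Step 1: the matching coefficient.** Let u be uptake, m the matched share of users, p_d abstinence on either drug and p_0 abstinence on none. With no matching effect, matched and mismatched users both have p_d. Then

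P(abstinent | no) = [u(1−m)p_d + (1−u)p_0] / (1−um),

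and non-users make up (1−u)/(1−um) of the no group.

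Take u = 0.60, m = 0.5, p_d = 0.25, p_0 = 0.10. Non-users are 0.40/0.70 = 57% of the no group. Abstinence there is (0.30×0.25 + 0.40×0.10)/0.70 = 0.164. The odds ratio is (0.25/0.75)/(0.164/0.836) = 1.70. Matched against mismatched users gives 1.00. Other pairs (p_d, p_0) give 1.50 for (0.20, 0.10), 1.40 for (0.25, 0.15) and 1.88 for (0.30, 0.10). If p_d = p_0, or if everyone uses a drug, the odds ratio is 1.00.

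**Step 2: the product term.** The same formula in each SES group, with p_d = 0.25 and p_0 = 0.10 except in the last row:

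| Setting (low/high SES) | Abstinence in no group | Odds ratios | Ratio low/high |
|---|---|---|---|
| Uptake 50/70%, m = 0.5 | 0.150 / 0.181 | 1.89 / 1.51 | 1.25 |
| Uptake 70/50%, m = 0.5 | 0.181 / 0.150 | 1.51 / 1.89 | 0.80 |
| Uptake 40/80%, m = 0.5 | 0.138 / 0.200 | 2.09 / 1.33 | 1.57 |
| Uptake 60/60%, m = 0.4/0.7 | 0.171 / 0.147 | 1.62 / 1.94 | 0.83 |
| Uptake 50/70%, m = 0.3/0.7 | 0.162 / 0.162 | 1.73 / 1.73 | 1.00 |
| Uptake 60/60%, m = 0.5, p_d = 0.15/0.30 | 0.121 / 0.186 | 1.28 / 1.88 | 0.68 |

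The ratio moves with uptake, matched share or drug effect, in either direction. Adding an arm term at 40/80% leaves it at 1.57 if arm does not change drug choice.

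**Step 3: the test.** In simulations at N = 100 with equal SES groups and no matching effect (4,000 trials per setting, assumed 5% level, inestimable fits counted as non-rejections), the interaction test rejected in 2.8% to 5.4% of trials. The median 95% interval ran about 9- to 12-fold either way.

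**Step 4: does three-level coding isolate matching?** Splitting none, mismatched and matched by SES gives 1.00 in every row of Step 2, but only because both drugs were given equal abstinence. Assume instead 30% on varenicline and 20% on patch whatever the metabolizer type, with half of users choosing each drug. With a fraction f of fast metabolizers, matched users quit at 0.30f + 0.20(1−f) and mismatched users at 0.20f + 0.30(1−f).

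- High SES, f = 0.70: 0.27 vs 0.23, odds ratio 1.24.
- Low SES, f = 0.40: 0.24 vs 0.26, odds ratio 0.90.
- Ratio 0.90/1.24 = 0.73, with no matching effect.

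Being matched mixes drug with metabolizer type, so these must be separated too.

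**Step 5: precision of arm-by-SES.** With 25 per cell, the standard error of the log ratio of odds ratios is √Σ 1/[25p(1−p)]. For assumed abstinence 0.25, 0.15, 0.25 and 0.20 this is √(0.213 + 0.314 + 0.213 + 0.250) = 1.00. At a two-sided 5% level, 80% power needs a ratio of about exp(2.80×1.00) ≈ 16.

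**The case against.** The best defence is that the SAP says what its variable is. Receiving the matched drug versus not receiving it is a real contrast, and the protocol's premise is that precision care raises both uptake and effectiveness, so one variable combining them suits a pragmatic pilot. This stands: 25% against 16.4% is a correct description of that composite. What does not follow is the sentence attributing the product term to matching.

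For H3.3, the SAP has an indirect route: Aim 2 tests arm on matching, and the moderation model tests matching by SES on abstinence. That addresses the proposed mechanism, and an arm-by-SES term would not show that matching is the mechanism. But the hypothesis is worded against standard care, and only an arm contrast is protected by randomisation.

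A reader might infer three stronger things that the documents do not support.

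- *The model is biased towards the hypothesis.* That needs, for example, lower uptake in low SES with equal matched shares. The protocol's background reports less treatment use and more safety concern among underserved smokers, but the trial offers medication to everyone, and "the patient can be referred to the Delaware Quitline for no-cost medications". An in-trial gap is an assumption, and the ratio can be below or equal to 1.
- *False positive findings are inflated.* The simulated rejection rates do not show this at about 100 participants.
- *Three-level coding is a complete cure.* Step 4 shows that it is not.

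**Conclusion.** The concern holds in a limited form. By its wording, the yes/no coding joins non-users and mismatched users, so the moderation model describes use of the matched drug versus everything else, and the planned inference about matching does not follow from it. The illustrative shifts (matching odds ratio 1.70; interaction ratios from 0.68 to 1.57 in the settings shown, including 1.00) rest wholly on assumed uptake, matched shares and abstinence rates, none of which the documents give. The sponsor may intend a comparison among users only, but the text does not say so.

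Separately, H3.3 as worded has no planned arm-by-SES or arm-by-race estimate.

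Severity is minor. The analysis is exploratory, its intervals will be very wide whatever the coding, and Aims 1 and 2 do not use this model, so nothing here casts doubt on the main arm comparisons.

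**What to change.** 1. **H3.3.** In all randomised participants, report arm-by-SES and, separately, arm-by-race estimates for abstinence with 95% confidence intervals and few or no further covariates. Label them exploratory, and state that they do not show matching to be the mechanism.
2. **Matching.** Report three levels (no medication, mismatched, matched) by SES, and read matching only from matched versus mismatched users. Include terms for drug and metabolizer group, with their SES products if estimable, or show a descriptive table by drug, metabolizer group and SES. Label the result observational, because drug choice follows randomisation.
3. **Inference sentence.** If the yes/no coding is kept, say that the product term compares use of the matched drug with all other participants, not matching as such.
4. **Sparse data.** Use a Firth fit, or descriptive tables alone.

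The cost is SAP wording only: arm, nicotine metabolite ratio, medication use, race and SES are already collected. The downside is precision. Under the assumed rates, 100 participants at 60% uptake give about 60×0.25 + 40×0.10 = 19 quitters. In simulation, the arm-by-SES ratio had a median 95% interval about 8.4-fold either way without covariates. The matched versus mismatched comparison had an interval about 3.4- to 3.9-fold either way, and at least one SES cell was empty or all-or-none in 8% to 22% of trials. Drug and metabolizer terms will thin the cells further. These results can be described, not tested.
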